14 INTERIM ANALYSIS AND DMC

No interim analysis is planned. No DMC is required for this study.

16 APPENDIX

16.1 PARTIAL DATE IMPUTATION: Algorithm for Prior/Concomitant Medications

Imputed dates will not be presented in the listings

• START DATE	• STOP DATE	• ACTION
Known	Known	
If start date < earliest dose date and stop date >= Visit 1, assign as prior.
 
If start date <= (latest dose date + 2 days) and stop date >= earliest dose date, assign as concomitant.
 
If start date <= end of study and stop date > (latest dose date + 2 days), assign as post-dose.

• START DATE	• STOP DATE	• ACTION
	Partial	
 Impute stop date as latest possible date (e.g. last day of month if day unknown or 31st December if day and month are unknown), then: 
 If start date < earliest dose date and stop date >= Visit 1, assign as prior. If start date <= (latest dose date + 2 days) and stop date >= earliest dose date, assign as concomitant. If start date <= end of study and stop date > (latest dose date + 2 days), assign as post-dose.
	Missing	
If start date < earliest dose date, assign as prior.
 
If start date <= (latest dose date + 2 days), assign as concomitant.
 
If start date <= end of study, assign as post-dose.

Partial	Known	
 Impute start date as earliest possible date (e.g. first day of month if day unknown or 1st January if day and month are unknown), then: 
 If start date < earliest dose date and stop date >= Visit 1, assign as prior. If start date <= (latest dose date + 2 days) and stop date >= earliest dose date, assign as concomitant. If start date <= end of study and stop date > (latest dose date + 2 days), assign as post-dose.
	Partial	
 Impute start date as earliest possible date (e.g. first day of month if day unknown or 1st January if day and month are unknown) and stop date as latest possible date (e.g. last day of month if day unknown or 31st December if day and month are unknown), then: 
 If start date < earliest dose date and stop date >= Visit 1, assign as prior. If start date <= (latest dose date + 2 days) and stop date >= earliest dose date, assign as concomitant. If start date <= end of study and stop date > (latest dose date + 2 days), assign as post-dose.

• START DATE	• STOP DATE	• ACTION
	Missing	
 Impute start date as earliest possible date (e.g. first day of month if day unknown or 1st January if day and month are unknown), then: 
 If start date < earliest dose date, assign as prior. If start date ≤ (latest dose date + 2 days), assign as concomitant. If start date ≤ end of study, assign as post-dose.
Missing	Known	
 If stop date ≥ Visit 1, assign as prior. If stop date ≥ earliest dose date, assign as concomitant. If stop date > (latest dose date + 2 days), assign as post-dose.
	Partial	
 Impute stop date as latest possible date (e.g. last day of month if day unknown or 31st December if day and month are unknown), then: 
 If stop date ≥ Visit 1, assign as prior. If stop date ≥ earliest dose date, assign as concomitant. If stop date > (latest dose date + 2 days), assign as post-dose.
	Missing	Assign as prior, concomitant, and post-dose.

16.2 PARTIAL DATE IMPUTATION: Algorithm for Treatment Emergence of Adverse Events

Imputed dates will not be presented in the listings

• START DATE/TIME	• STOP DATE/TIME	• ACTION
• Known	• Known	
 If start date/time < dose date/time, then not TEAE. 
 If start date/time ≥ dose date/time and < (dose date/time + 48 hours (or 2 days)), then TEAE
•	• Partial	
 If start date/time < dose date/time, then not TEAE.

• START DATE/TIME	• STOP DATE/TIME	• ACTION
		
 • If start date/time \geq dose date/time and $<$ (dose date/time + 48 hours (or 2 days)), then TEAE.
•	• Missing	
 • If start date/time $<$ dose date/time, then not TEAE. • If start date/time \geq dose date/time and $<$ (dose date/time + 48 hours (or 2 days)), then TEAE.
• Partial, but known components show that it cannot be on or within 48 hours after dose date/time	• Known	• Not TEAE.
•	• Partial	• Not TEAE.
•	• Missing	• Not TEAE.
• Partial, could be on or within 48 hours after dose date/time	• Known	
 • If stop date/time $<$ dose date/time, then not TEAE. • If stop date/time \geq dose date/time, then TEAE.
•	• Partial	
 • Impute stop date/time as latest possible date/time (e.g. last day of month if day unknown or 31st December if day and month are unknown), then: 
 • If stop date/time $<$ dose date/time, then not TEAE. • If stop date/time \geq dose date/time, then TEAE.
•	• Missing	• Assumed TEAE.
• Missing	• Known	
 • If stop date/time $<$ dose date/time, then not TEAE.

• START DATE/TIME	• STOP DATE/TIME	• ACTION
		
 If stop date/time \geq dose date/time, then TEAE.
•	• Partial	
 Impute stop date/time as latest possible date/time (e.g. last day of month if day unknown or 31st December if day and month are unknown), then: 
 • If stop date/time $<$ dose date/time, then not TEAE. • If stop date/time \geq dose date/time, then TEAE.
	Missing	
 Assumed TEAE.

16.3 DATA HANDLING RULES OF EFFICACY AND EXPLORATORY ANALYSIS FOR E-E-DIARY AND CRF DATES AND TIMES

As described in Section 5.4, Scenario #6 subjects will be included in efficacy analysis with respect to e-diary dates and times and their relative post-dose assessments times under below rules if their respective CRF date does not match.

Subjects with partial dates entered on CRF with missing time of dosing for first dose on CRF that do not contradict the e-diary date. These subjects will be considered for efficacy analysis with respect to e-diary date and time.

Subjects with CRF first dose date is after subject answered the question for 0.5 time point due to which the questions in the e-diary look appropriate with respect to e-diary first dose date. These subjects will be considered for efficacy analysis with respect to e-diary date and time.

Subjects with indication in CRF that they had taken first dose prior to all migraine start times recorded in e-diary due to which first dose e-diary date becomes closer to or after last migraine start in the e-diary. These subjects will be considered for efficacy analysis with respect to e-diary date and time.

Subjects with different first dose times in e-diary vs on CRF. If the e-diary data is not entered retroactively by subject, then e-diary first dose dates will be in accordance with assessments completed by subject. These subjects will be considered for efficacy analysis with respect to e-diary date and time.

Subjects with CRF dates for 2nd dose are entered more than 24 hours after first dose. These subjects will be considered for efficacy analysis with respect to e-diary date and time.

Subjects with indication in CRF that they had taken second dose prior to all migraine start times recorded in e-diary due to which second dose e-diary date becomes closer to or after last migraine start in the e-diary. These subjects will be considered for efficacy analysis with respect to e-diary date and time.

Subjects with indication of taking second dose on CRF with CRF date and time but second dose date is not in e-diary. Due to this, some first dose data from e-diary assessments before time of second dose on CRF will be used for analysis. These subjects' first dose data will be considered for efficacy analysis with respect to e-diary date and time.

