
### 9.2.2 Treatment Emergent Adverse Events (TEAE)

A TEAE will be an AE that occurred during the study after the first dose of study drug or that was present prior to dosing and exacerbates after the first dose of study drug.

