The start and end of treatment exposure for efficacy and safety analysis will always be identified from the first and last dates of dosing entered in the e-diary, when available and appear to be analysis useful data. As mentioned before if cases like those described in detailed Scenarios #4, #5 and #7 in Section 5.4 leave e-diary dates missing, alternatives from the CRF data will be used for first and second dose dates for safety analysis if there is a confirmation of dosing in the CRF. In some cases if e-diary dates appear to be out of order (CRF dates are clear legitimate corrections of e-diary for first dose and second dose), i.e.: second dose date and/or time recorded in e-diary is before first dose date and/or time; same first and second dose dates and time in e-diary, such dates and/or time will be corrected by CRF data as provided by the subject at Visit 2/EoS. These will be the exceptions where CRF dates will be considered for safety analysis. Otherwise, if the CRF dates and e-diary dates do not match, then for overall treatment exposure, earliest date available from CRF or e-diary will be considered for start of exposure and latest date available from CRF or e-diary will be considered for end of exposure. Additionally, for first dose exposure, earliest date available from CRF or e-diary will be considered for start of exposure of first dose and latest date will be considered for end of exposure of first dose. Similarly, for second dose exposure, earliest date available from CRF or e-diary will be considered for start of exposure of second dose and latest date will be considered for end of exposure of second dose. If the first dose date is missing from the e-diary data as well as CRF data but CRF has a confirmation of first dose, the eligibility-confirmation date will be used as the first alternative for safety analyses, and the randomization date will be the second alternative for safety analyses. If the confirmation of second dose is available on CRF but the second-dose date is missing in e-diary as well as CRF, the alternative will be the study-completion/discontinuation date from the Discontinuation form for safety analysis. Subjects lost to follow-up with no information on dosing on e-diary will be excluded from safety analysis.

The statistical evaluation will be performed using SAS version 9.4 or higher.

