12.1 Adverse Events

An adverse event (AE) with the date/time of onset, or that worsens in intensity, at or within 48 hours after the time of dosing with study drug will be considered a TEAE. AEs with a missing start date will be assumed to be treatment-emergent, except as described in Appendix 1. If a subject takes at least one dose of study drug, but the date and time of dosing is missing in the e-diary, all AEs for that subject will be considered treatment-emergent, if the AEs occur between available date of dosing as recorded only in CRF for up to 48 hours (2 days) post recorded date of dosing. If the date and time of the second dose is missing in e-diary then all AEs for that subject will be considered as treatment emergent due to second dose, if AEs occur between available date of dosing in CRF for second dose, and an ending boundary of 2 days after recorded date of dosing with second dose, inclusive. See Appendix 1 for derivations related to partial dates and times.

Nausea and/or vomiting reported as adverse events during a migraine by any subject that also noted these as characteristics of their migraine will be compared against placebo and may not be considered related to treatment but rather an underlying condition of the migraine.

AEs will be coded by the Medical Dictionary for Regulatory Activities (MedDRA) version 18.0.

Unless otherwise stated, frequencies of adverse events will be displayed by applicable treatment group and overall. AEs will be sorted alphabetically by system organ class (SOC) and then preferred term (PT) by frequency. For the overall summary of AEs, both subjects ever experiencing an event, as well as total events, will be presented. For all other summaries, subjects with multiple occurrences of the same AE preferred term will be counted once within the corresponding system organ class and preferred term.

Adverse events will be summarized in the following tables:

- Overall summary of AEs, including:
 - AEs
 - TEAEs
 - Related TEAEs
 - TEAEs leading to study discontinuation
 - Serious TEAEs
 - Related serious TEAEs
 - TEAEs leading to death
- Incidence of TEAEs
- Incidence of TEAEs by relationship to study drug
- Incidence of TEAEs by maximum severity
- Incidence of AEs leading to study discontinuation
- Incidence of related AEs leading to study discontinuation
- Incidence of TEAEs leading to death
- Incidence of serious TEAEs
- Incidence of serious TEAEs by relationship to study drug

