12.1.1 Relationship to Study Drug

Summaries of AEs by relationship to study drug will classify AEs as either:

- Reasonably or Possibly Related
- Not Reasonably or Possibly Related

Related AEs are those that are recorded on the AE CRF page as “Reasonably or Possibly Related” or those with a missing relationship.

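### SAP 16.2 has no branch for adverse events that worsen after dosing, contrary to SAP 12.1 and the protocol; and for the few doses with no recorded date, surrogate dates can misplace the 48-hour TEAE window

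*SAP*

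**What the plan says.** **Definition.** SAP 12.1 makes a TEAE of "An adverse event (AE) with the date/time of onset, or that worsens in intensity, at or within 48 hours after the time of dosing". Protocol 9.2.2 reads "A TEAE will be an AE that occurred during the study after the first dose of study drug", and adds an event that "was present prior to dosing and exacerbates after the first dose of study drug". Protocol 10.8.1 also includes worsening, within 48 hours of a dose.

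**Algorithm.** For an AE with a known start, SAP 16.2 says "If start date/time < dose date/time, then not TEAE". The rule is the same whether the stop date is known, partial or missing. A start at or after the dose is a TEAE only if it is strictly less than 48 hours (or 2 days) later.

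**Undated doses.** If the e-diary lacks the dose date, SAP 12.1 uses the CRF date. If both sources lack it but the CRF confirms dosing, SAP 5 provides substitutes. For the first dose, "the eligibility-confirmation date will be used as the first alternative for safety analyses, and the randomization date will be the second alternative". For the second dose, "the alternative will be the study-completion/discontinuation date from the Discontinuation form for safety analysis".

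**Relatedness.** SAP 12.1 says that nausea or vomiting that was also a feature of the subject's migraine will be compared against placebo and "may not be considered related to treatment but rather an underlying condition of the migraine". SAP 12.1.1 has no such exception. It begins "Related AEs are those that are recorded on the AE CRF page as", names the related category, and adds events whose relationship is missing.

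**The concern.** The TEAE tables are the main safety output. A definition and an algorithm that disagree can be programmed in two ways and give two sets of counts. AEs are collected from consent (protocol 9.2.1), and a subject may wait weeks for an attack, so some AEs will already be present at dosing. Whether their worsening counts should not depend on which section the programmer follows.

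The surrogate dates raise a second problem. A deliberately early dose date is cautious only when the window after it is open-ended. With a 48-hour limit, an early date can close the window before the real dose. A date at study end opens the window about when AE collection stops. Second-dose safety is a stated objective (protocol 5.4), so allocation of events between the two doses matters.

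**Working it through.** The plan states no figure to reproduce here. The check compares the two rules on test events and then works out where the surrogate windows fall.

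**1. SAP 12.1 against SAP 16.2** (known start, hours relative to dose)

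| Event | SAP 12.1 | SAP 16.2 |
|---|---|---|
| Onset −24 h, worsens +1 h | TEAE | not TEAE |
| Onset −24 h, no worsening | not TEAE | not TEAE |
| Onset +1 h | TEAE | TEAE |
| Onset +47.9 h | TEAE | TEAE |
| Onset exactly +48 h | TEAE | no class |

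The rules disagree in the first and last rows.

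**2. First dose undated in both sources.** Let g be the days from the eligibility call to the real dose; protocol 5.6.3 allows up to 8 weeks, so g runs from 0 to 56. An AE starting 1 h after the real dose lies 24g + 1 hours after the surrogate date:
- g = 0: 1 h, inside the window.
- g = 1: 25 h, inside.
- g = 2: 49 h, outside, as for every larger g.

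How often g reaches 2 days cannot be read from the documents. As an illustration, assume attacks arrive at a constant rate r per month of 30.4375 days, with r from 3 to 8 (inclusion criterion 6). The chance that the window misses the dose is exp(−2r/30.4375):
- r = 3: exp(−0.197) = 0.821.
- r = 8: exp(−0.526) = 0.591.

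If the randomization date is used and the call comes c days later, with no dosing before the call, the chance is exp(−r × max(0, 2 − c)/30.4375). For c = 1 this is 0.906 (r = 3) or 0.769 (r = 8). For c of 2 or more it is 1. All these figures are conditional on a subject needing the fallback.

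The error can also go the other way: an AE that starts a few hours after the call, days before the real dose, falls inside the surrogate window and becomes a TEAE.

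**3. Second dose undated in both sources.** Let the real second dose be t hours after the first, with t from 2 to 24 as the protocol allows. Its 48-hour window ends 48 + t hours after the first dose; the first-dose window ends at 48. SAP 12 runs first-dose AE summaries up to the second dose, here placed at study end. So:
- Onsets between t and 48 h are counted as first-dose TEAEs: misallocated, not lost.
- Onsets between 48 and 48 + t h belong to neither window and drop out. This slice is (48 + t) − 48 = t hours, that is 2 to 24 of the 48 hours, ending at the latest at 48 + 24 = 72 h.

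Example: an onset at 25 h with study end at 7 days (168 h) is not a second-dose TEAE (25 < 168), but it is a first-dose TEAE (25 < 48).

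**4. Nausea and vomiting.** The sentence in 12.1 concerns causality. Nothing in 12.1 or 16.2 removes these events from TEAE incidence. The related-TEAE tables, however, could follow either 12.1 or 12.1.1, and 12.1 gives no criterion for re-attribution.

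**The case against.** **The appendix is only for partial dates.** Its title says so, SAP 12.1 refers to the appendix for missing and partial dates, and 12.1 holds the definition, so 12.1 may be meant to govern. This is plausible but not stated. The first row of 16.2 covers fully known start and stop dates, so it also sets a rule for complete data.

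**A worsening may be entered as a new AE.** Protocol 9.2.1 makes a clinically significant exacerbation of a pre-existing condition an AE after treatment. If it were given its own start date, 16.2 would catch it. No section says that it is, and protocol 10.8.1 and SAP 12.1.2 provide for several severities within one AE. The objection does mean that a reader should not infer that every worsened pre-dose event is lost.

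**The undated-dose case is narrow.** CRF dosing dates and times are to be completed for all subjects (SAP 5), so few may lack both sources. SAP 12.1 also never says that the surrogate dates anchor the 48-hour window; that is inferred from SAP 5 assigning them to safety analyses. Both points stand. AEs with a missing start, or a partial start that could fit the window, still default to TEAE unless they stopped before the dose. Only events with known onset are at risk.

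**The safety contrast.** A reader might infer that lasmiditan's excess over placebo is understated, given Phase 2 TEAE rates of 65–86% at the doses studied here against 22% on placebo (protocol 4.2). The documents do not support this. The rules apply to all arms, an early surrogate can add events as well as miss them, and the affected number is unknown. All AEs also appear in the overall summary and the listings.

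**Protocol 9.2.2 has no 48-hour limit.** True, but protocol 9.2.1, protocol 10.8.1 and SAP 12.1 agree on 48 hours, so the analysis window is not in doubt.

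**Conclusion.** The contradiction between SAP 16.2 and the TEAE definition is real. Coded literally, 16.2 misclassifies a pre-dose AE that worsens after dosing and leaves an onset at exactly 48 hours unclassified. The number of such events cannot be computed from the documents.

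The surrogate-date problem is real but conditional. It needs a confirmed dose with no date in either source, and a 48-hour window anchored on the substitute. AEs with known onset after the real first dose can then be missed. Second-dose AEs move to the first dose, or are lost if they start more than 48 hours after it. The 59–82% illustration for the eligibility date rests on an assumed constant attack rate and describes only that subset, whose size is not given; it must not be read as a share of the trial.

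It would also be wrong to read the nausea and vomiting sentence as lowering TEAE incidence. What remains is an unresolved rule for relatedness. The net direction of any bias is not established. This should be fixed before unblinding, because a safety table should not be programmable in two ways, but nothing shows that it threatens the trial's safety conclusions.

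**What to change.** (a) In SAP 16.2, add that an AE starting before the dose and worsening at or within 48 hours after any dose is a TEAE. Change the strict inequality at 48 hours to less than or equal, and state that 12.1 governs wherever the two differ.

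(b) For a confirmed dose with no date in either source, do not apply a 48-hour window to a surrogate date. For an undated first dose, count AEs from the eligibility call to end of study as TEAEs. For an undated second dose, also show AEs from the first dose to end of study in the second-dose tables. Flag these subjects and report how many there are.

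(c) State that related-TEAE tables use the CRF relationship as in 12.1.1. Present any re-attribution of nausea or vomiting to migraine only as a supplementary summary.

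The cost is SAP wording and a few lines of code. For the flagged subjects, the inclusive rule departs from the 48-hour definition and will count some unrelated events, including some that began before the real dose. The flag lets a reader see how much this matters.
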